## 3.3.4.3. Missing Severity Assessment for Adverse Events

If severity is missing for an AE that started before the date of the first dose of double-blind investigational product, then a severity of *mild* will be assigned. If the severity is missing for an AE that started on or after the date of the first dose of double-blind investigational product, then a severity of *severe* will be assigned. The imputed values for severity assessment will be used for the incidence summary, while the actual values will be presented in the data listings.

#### 3.3.4.4. Missing Relationship to Investigational Product for Adverse Events

A relationship of *unrelated* to investigational product will be assigned if the AE started before the administration of the first dose of double-blind investigational product. If the relationship to investigational product is missing for an AE that started after the administration of the first dose of double-blind investigational product, a causality of *definitely related* will be assigned. The imputed values for relationship to double-blind investigational product will be used for the incidence summary, while the actual values will be presented in the data listings.

#### 3.3.5. Imputation of Incomplete Dates

An incomplete date is any date for which either the day, month, or year is unknown, but all three fields are not unknown. An incomplete date occurs when the exact date an event occurred or ended cannot be obtained from a patient. For many of the analyses, a complete date is necessary in order to determine if the event should be included in the analysis (i.e., if the event is treatment-emergent) or to establish the duration of an event. In such cases, incomplete dates will be imputed.

To minimize bias, the project statistician will impute dates in a systematic but reasonable manner. The following rules for missing or partial event dates for events will be implemented. For incomplete event start dates, if the month/year is the same as the Day 1 month/year then the date will be set to the date of Day 1. In other cases, missing days will be imputed as the day component of Day 1; missing months/years will be imputed as the month/year of Day 1. If this method of imputation produces and invalid date, the last date of the month will be used. For incomplete end dates, the same process will be used, but using event start date to impute instead of Day 1. In the case where there is a known, complete event end date prior to Day 1, partial event start dates will be imputed using the event end date instead of Day 1.

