## Treatment-emergent Adverse Event

Any recorded adverse event that occurs on or after the initiation of study treatment and less than or equal to 14 days after the last dose of treatment is considered treatment-emergent. Additionally, it is assumed that an adverse event which was reported to have started on Day 1 without an associated onset time may have occurred after the initiation study treatment. Hence, adverse events occurring on Day 1 without an onset time are assumed to be treatment emergent.

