#### 5.4.1. Adverse Events

Adverse events will be mapped to a Medical Dictionary for Regulatory Activities (MedDRA) version 20.1 preferred term and system organ classification. If a patient experiences multiple events that map to a single preferred term, the greatest severity grade and strongest investigator assessment of relation to study medication will be assigned to the preferred term for the appropriate summaries. As noted in Section 3.3.4.3 and Section 3.3.4.4, should an event have a missing severity or relationship, it will be classified as having the highest severity ("severe") and/or strongest relationship to study medication ("definitely related") if it is deemed treatment-emergent.

A summary of adverse events will provide an overview of the number of patients that experienced a TEAE and the total number of TEAEs observed within those patients. Similar summary measures will be included to display the number of patients and corresponding events within events that were related to study drug, were serious, led to discontinuation of study drug, or led to death.

The occurrence of TEAEs will be summarized by treatment group using preferred term, System Organ Classification (SOC), and severity. Separate summaries of treatment-emergent serious adverse events, treatment-emergent adverse events related to study treatment, treatment-emergent adverse events leading to discontinuation of study treatment, and treatment-emergent fatal adverse events will be generated. All adverse events reported will be listed for individual patients showing both verbatim and preferred terms, as well as SOC. All adverse events that occurred prior to the initiation of study treatment will be excluded from the tables but will be included in the listings.

TEAEs of special interest will be tabulated if any are observed. Adverse events of special interest (AESI) are:

- Palpitations or abnormal heart rhythms
- · Dizziness or syncope
- Seizure

Missing onset dates will be imputed as previously outlined in Section 3.3.5 as required to determine treatment-emergent events. Adverse events occurring on Day 1 with missing onset times will be assumed to be treatment emergent.

An AE that occurs > 14 days after the date of the last dose of treatment will not be considered a TEAE but will be included in the patient data listings but not the summary tables.

Any patients that died, discontinued treatment due to a TEAE, or experienced an SAE will be listed separately.

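### SAP 3.3.5 fills an unknown start day with Day 1's day of the month, which can put an onset after its recorded end or move a true TEAE out of the window (minor correction)

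*SAP*

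**What the plan says.** SAP 3.3.5 has two rules for a start date with a missing day.

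- In the calendar month of Day 1: "if the month/year is the same as the Day 1 month/year then the date will be set to the date of Day 1".
- In any other month: "In other cases, missing days will be imputed as the day component of Day 1". Where that day does not exist in the month, the last day of the month is used.

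One safeguard involves the end date: with a "known, complete event end date prior to Day 1, partial event start dates will be imputed using the event end date" in place of Day 1. It does not apply to an event that ended on or after Day 1.

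SAP 5.4.1 gives these dates a purpose: "Missing onset dates will be imputed as previously outlined in Section 3.3.5 as required to determine treatment-emergent events". The window, in SAP 3.3.8, takes in any event that "occurs on or after the initiation of study treatment and less than or equal to 14 days after the last dose of treatment". Under SAP 5.4.1, an event dated later than that appears in the listings but not in the summary tables. Protocol 10.8.1 describes the double-blind adverse-event set as events with onset in the 12-week period.

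**The concern.** Once an event falls in a month after Day 1's month, the inserted day depends only on when the patient was randomised. A patient who started on the 25th has every such event dated the 25th (or the last day of a shorter month), even if the event ended on the 5th. Nothing stops the imputed start from passing the recorded end date or the end of the treatment-emergent window.

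Two things are at stake. Dates in which the start follows the end are impossible on their face and have to be resolved by someone. More importantly, an event close to early discontinuation can lose its treatment-emergent status through the imputation alone. Early stopping should be expected here: Protocol Table 2 reports that 165 of 244 randomised patients completed the double-blind phase of the Phase 2b study, so 79/244 = 32% did not.

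The rule also runs against the rest of the SAP. Elsewhere doubt is resolved towards counting the event. Missing severity on treatment becomes severe (3.3.4.3), and missing relationship becomes definitely related (3.3.4.4). A Day 1 event without an onset time is treatment-emergent (3.3.8), and a partial date in Day 1's month becomes Day 1 (3.3.5).

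**Working it through.** The documents state no figure on this point, so there is none to reproduce. The check applies the written rule to single cases and then enumerates it.

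**Inputs**

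- Imputation rule, last-day-of-month rule and end-date safeguard: SAP 3.3.5.
- Treatment-emergent window, first dose to last dose + 14 days: SAP 3.3.8 and 5.4.1.
- Week 12 target day, Day 85: SAP Table 1. Extension dosing starts the day after Week 12: Protocol 3.1.
- Assumptions, not in the documents: every Day 1 date in 2018–2019 equally likely (730 dates); onset days equally likely; only the day of the month missing; event durations of 1 to 28 days; early stoppers' last dose equally likely on Days 14–84.

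**Rule as coded.** Let D be the day of the month of Day 1. For onset month m other than Day 1's month, imputed start = min(D, number of days in m) of month m. In Day 1's month, imputed start = Day 1. If a known end date is before Day 1, the end date replaces Day 1 as the reference.

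**(a) Start after recorded end.** Day 1 is 20 January 2019, the start is recorded as March 2019 with the day unknown, and the end is 10 March 2019. The end is after Day 1, so the safeguard does not apply. Imputed start = 20 March, which is 20 − 10 = 10 days after the event ended.

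Over all Day 1 dates and true onsets on Days 1–85, the share with imputed start later than true end is:

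| Event duration | Share |
|---|---|
| 1 day | 45% |
| 3 days | 41% |
| 5 days | 37% |
| 7 days | 33% |
| 14 days | 17% |
| 28 days | 0.5% |

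**(b) TEAE lost in an early stopper.** Day 1 is 25 January 2019 and last dose is 20 February (Day 27). The window closes on 20 February + 14 days = 6 March. An event that truly began on 3 March, recorded as March with the day unknown, is imputed to 25 March. That is 33 days after last dose, so the event is no longer treatment-emergent.

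The share of true, day-missing TEAEs that the rule drops is:

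| Last dose on | All TEAEs | Onset in the 14 days after last dose |
|---|---|---|
| Days 14–84 | 8% | 30% |
| Days 1–84 | 9% | 32% |

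**(c) Completers, double-blind tables.** Day 1 is 20 January 2019, so Day 85 is 14 April. An event that truly began on 5 April (Day 76), recorded as April with the day unknown, is imputed to 20 April = Day 91. In the enumeration, every double-blind event moved past Day 85 lands on Days 90–93. Two readings follow:

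- *Onset must fall by Day 85 (a strict reading of Protocol 10.8.1):* 10.8% of day-missing double-blind events leave the double-blind tables, and 32% of those with onset on Days 57–85.
- *Last double-blind dose + 14 days:* with the last dose on Day 84 the window runs to 84 + 14 = Day 98. Days 90–93 lie inside it, so 0% are lost.

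**The case against.** Several points on the other side stand.

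- *No planned output uses duration.* SAP 3.3.5 mentions duration as a reason to impute, but neither 5.4.1 nor the output list in Section 9 contains an adverse-event duration analysis. In a patient who continues treatment, a start later than the end does not by itself change treatment-emergent status. The 45% is also the least realistic case: for a 1-day event, a known end date already gives the start. The 7- and 14-day figures are the fairer ones.
- *The 30% is a selected slice.* Across all day-missing TEAEs in early stoppers the loss is about 8%.
- *Few dates should be affected.* Through Week 12 there is a site visit or a scheduled call every week (Protocol time and events schedule), so unknown onset days should be uncommon. Excluded events remain in the listings.
- *The completer effect is conditional.* The SAP gives no explicit rule for assigning events to a phase in patients who roll over, and one plausible rule removes the effect.

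A reader might also infer that placebo-period events are moved into a MIN-101 open-label column and so bias the comparison against the drug. The documents do not support this. SAP 5.5 summarises cumulative data over the 52 weeks by treatment sequence, so a placebo patient's event stays in a placebo-to-MIN-101 column whatever day is imputed. The shift is not universal either. In about 79% of the 730 Day 1 dates, the imputed day in the month of the first open-label dose falls after that dose. For Day 1 in roughly the first five days of a month, some early open-label events are pulled the other way.

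These points limit the size of the problem. They do not answer (a), which is an impossible date, or (b), which follows from the SAP's own definitions.

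**Conclusion.** The rule is wrong as written, and a minor correction is warranted. Taken literally, SAP 3.3.5 can date an onset after its own recorded end, and in early stoppers it can remove a true TEAE from the summary tables (about 8% of their day-missing TEAEs, about 30% of those in the 14 days after last dose). Under a strict 12-week onset cut-off, about 11% of completers' day-missing double-blind events also leave the double-blind tables; under last double-blind dose + 14 days, none do.

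All percentages are shares of events with only the start day missing, under uniform Day 1 and onset dates and, for (a), assumed durations. They are not shares of all adverse events. The documents give no count of partial dates, and the absolute effect is probably small. No distortion of the arm comparison through open-label columns is claimed.

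**What to change.** Add to SAP 3.3.5:

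1. An imputed start date may not be later than a known end date.
2. If the known month and year overlap the treatment-emergent window (first dose to last dose + 14 days) and no recorded information excludes onset within it, the event is treated as treatment-emergent.
3. If the known month contains the first open-label dose, the same principle applies with the double-blind window, using the recorded end date where there is one. The SAP should state whether that window ends with the 12-week period or at last double-blind dose + 14 days.

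First-of-month imputation alone should not be the remedy. It removes (a) and (b), but under a Day 85 cut-off it would place about 52% of day-missing events from the first four open-label weeks in the double-blind phase, against about 3% under the present rule.

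The cost is a few lines of SAP text and programming, with no new data. The downside is that slightly more events may count as treatment-emergent, which is the direction the SAP already takes for missing severity, relationship and onset time.

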#### 3.3.6. Imputation of Alphanumeric Data

Should there be instances where a clinical laboratory parameter is reported with imbedded non-numeric characters, as for example, "<0.1" or ">10", the data will be imputed for the purpose of quantitative summaries. The actual values as reported in the database will be presented in data listings.

For incorporation in quantitative summaries, the following imputation rules will be employed:

The limit of quantitation will be increased by one level of precision in the direction of the symbol that precedes the value. For example, "<0.1" will be imputed to "0.09", while ">0.1" will be imputed to "0.11", and ">10" will be imputed to "10.1". Values reported as "\le " or "\ge " will be imputed similarly. For example, "\le 0.1" will be imputed to "0.09".

## 3.3.7. Presentations by Time Point

Visit designations used in statistical analyses will be derived by aligning actual visit dates within visit date windows as shown in Table 1. If assessments are collected multiple times within a given visit window, the result closest to the target day will be used for summary presentations. If two measurements have the same distance to the target day, the earlier value will be used. All planned, Unscheduled, and Early Termination assessments will be categorized similarly. All assessments will be presented in the listings.

Table 1 Visit Designations

Derived Visit	Scheduled Visit (Day a )	a Target Day						
Baseline	Day -1		Days [-28, 1] and prior to first dose of study drug					
Day 1	Day 1	1	Day [1]					
Day 2	Day 2	2	Day [2]					
Week 1	Week 1	8	Days [3,11]					
Week 2	Week 2	15	Days [12, 18]					
Week 3	Week 3	22	Days [19, 25]					
Week 4	Week 4	29	Days [26, 43]					

Derived Visit	Scheduled Visit (Day a )	Target Day	Window [lower bound, upper bound] b				
Week 8	Week 8	57	Days [44, 71]				
Week 12 End of double- blind treatment period c	Week 12	85	Days 72 through last day of double-blind treatment period.  Final or termination visit during the double-blind treatment phase				
Week 12.1	Week 12 + 1	87	First day of open-label treatment				
Week 12.2	Week 12 + 2	88	First day of open-label treatment + 1				
Week 13	Week 13	92	First day of open-label treatment + 2 through Day 9				
Week 14	Week 14	99	Days [96, 102]				
Week 15	Week 15	106	Days [103, 109]				
Week 16	Week 16	113	Days [110, 127]				
Week 20	Week 20	141	Days [128, 155]				
Week 24	Week 24	169	Days [156, 183]				
Week 28	Week 28	197	Days [184, 211]				
Week 32	Week 32	225	Days [212, 239]				
Week 36	Week 36	253	Days [240, 267]				
Week 40	Week 40	281	Days [268, 295]				
Week 44	Week 44	309	Days [296, 323]				
Week 48	Week 48	337	Days [323, 351]				
Week 52	Week 52	365	Days [352, 372]				
Week 54 EOS period c			Final or termination visit during the open-label treatment period; date will be earlier if early study termination occurred.				

a Relative to the date of the first dose of double-blind investigational product. For example, Day 1 = the date of the first dose of double-blind investigational product. The lower and upper bounds reach approximately halfway between the windows. For example, weekly visit series use windows that are [-3 days,+3 days] surrounding each target day. However, visit windows leave no gaps in time for assessments to be uncategorized.

b Visit day is calculated as (visit date – date of the first dose of double-blind investigational product + 1) if the visit date is on or after the date of the first dose of double-blind investigational product. Otherwise, it's calculated as (visit date – date of the first dose of double-blind investigational product).

e Presented in analysis tables for safety parameters, including but not limited to electrocardiographic parameters, clinical laboratories, and vital signs.

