## Derived Study Visit

Derived Study Visit is the visit designation reflective of when an actual study assessment was measured, as defined in Section 3.3.7. When compliance with the planned schedule of visits is good, the derived study visit will be the same as the scheduled study visit. The derived study visits re-classifies visits that occur off schedule.

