#### Change from Baseline

Change from Baseline for a given endpoint is defined as the Derived Study Visit X value minus the Baseline Value.

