#### 5.2. EFFICACY ANALYSIS

The efficacy analyses will be based on the ITT Population, although they will also be performed for the PP population for comparison.

[figure not shown]
All efficacy parameters will be summarized descriptively by treatment arm and visit, as appropriate. All statistical tests will be 2-sided hypothesis tests performed at the 5% level of significance. All confidence intervals will be 2-sided 95% confidence intervals unless stated otherwise.

Additionally, by-visit analyses will be carried out for all efficacy parameters as deemed applicable using the mixed-effects model for repeated measures (MMRM).

Sensitivity analyses will be performed to better understand the impact of missing data and/or imputation of the primary efficacy endpoint, as described in Section 3.3.4.2.

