## 5.2.1. Primary Estimand

The primary estimand, the main clinical quantity of interest to be estimated in the study, is defined by the following components:

**Population**: Stable patients with schizophrenia with a predefined minimum PANSS negative symptom score before randomization.

**Endpoint**: Change in the PANSS Marder NSFS from Baseline to the end of Week 12.

The NSFS consists of the sum of the ratings (on a scale of 1-7, from least to highest severity of psychopathology) across the PANSS items N1, N2, N3, N4, N6, G7, and G16. Thus, each assessment is a number between 7 and 49.

N1. Blunted affect

N2. Emotional withdrawal

N3. Poor rapport

N4. Passive/apathetic social withdrawal

N6. Lack of spontaneity

G7. Motor retardation

G16. Active social avoidance

**Measure of Intervention**: The effect of the initially randomized treatment that would have been observed had all patients remained on their treatment throughout the double-blind phase.

**Intercurrent events**: Early study discontinuation for any reason.

**Summary measure**: Difference in treatment means.

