#### 5.2.2. Primary Efficacy Analysis

As noted in Section 3.3.4, no imputation of data elements will be performed for the primary analysis to be submitted to the US FDA. Pattern-mixture modelling imputation of missing primary endpoint data will be performed before conducting the primary analysis to submit within the EMA dossier. In both approaches, the estimand and analytic approach of using MMRM to evaluate the potential treatment effects is the same, but the data used to analyze the estimand is different between the US FDA and EMA dossiers.

The PANSS Marder NSFS scores and change from Baseline will be summarized by treatment group and study visit. In addition, the trend in change from Baseline in Marder NSFS scores over the series of visit assessments will be presented graphically.

Change from Baseline to Week 12 in the PANSS Marder NSFS score will be analyzed using a MMRM with fixed effects for treatment group (MIN-101 64 mg, MIN-101 32 mg, and placebo), region, visit, and treatment-by-visit interaction, a random effect for patient within treatment group, and Baseline NSFS as covariate. An unstructured covariance matrix will be used to model the covariance of within-patient scores. The Kenward-Roger approximation will be used to estimate denominator degrees of freedom. Comparison against placebo will be performed with the MIN-101 64 mg and 32 mg doses.

The hypotheses can be expressed as follows:

```
Null Hypothesis (H_0): \muMIN-101 64 mg - \muControl = 0 and \muMIN-101 32 mg - \muControl = 0
```

Alternative Hypothesis (Ha):  $\mu$ MIN-101 64 mg -  $\mu$ Control  $\neq$  0 or  $\mu$ MIN-101 32 mg -  $\mu$ Control  $\neq$  0

where  $\mu$ MIN-101 64 mg and  $\mu$ MIN-101 32 mg refer to the mean change from Baseline to week 12 in the PANSS Marder NSFS score at each of the 2 experimental doses, and  $\mu$ Control refers to the mean change from Baseline to week 12 in the PANSS Marder NSFS score in the placebo arm.

As described in Section 3.3.3.1, the adjustment for multiplicity within the family of primary hypotheses will utilize the truncated Hochberg procedure for the purpose of reporting results. This procedure will allow the null hypothesis of no treatment difference for both the 64 mg and 32 mg doses versus placebo to be rejected if largest p-value of comparing either of these 2 doses versus placebo is at or below 0.05. Otherwise, the lowest of these 2 p-values must be at or below 0.025 reject the null hypothesis for the representative dose.

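### SAP Table 1 labels some early-termination PANSS and PSP scores at visits where the scale is not planned, so an MMRM run on the planned visits loses them

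*SAP*

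**What the plan says.** SAP 3.3.7 contains the SAP's only window table. Its scope is general: "Visit designations used in statistical analyses will be derived by aligning actual visit dates within visit date windows as shown in Table 1". Early termination gets no separate treatment: "All planned, Unscheduled, and Early Termination assessments will be categorized similarly". A Table 1 footnote adds that the windows leave no gaps, so every score receives a label.

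SAP 3.3.8 carries the label into the endpoint. Of derived visits it says "The derived study visits re-classifies visits that occur off schedule", and then: "Change from Baseline for a given endpoint is defined as the Derived Study Visit X value minus the Baseline Value".

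Table 1 has windows for Day 1, Day 2 and Weeks 1, 2, 3, 4, 8 and 12. The schedule in SAP 1.2 plans PANSS and CGI-S at Weeks 2, 4, 8 and 12, and PSP at Weeks 4, 8 and 12. Protocol 8.1.3.4 gives any patient who stops early the full Week 12 procedures, so PANSS and PSP can be rated on any day.

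SAP 5.2.2 and 5.2.5 put visit and treatment-by-visit in the model but do not list the visits. Protocol 10.5.1 bases the primary analysis on every observed post-Baseline score, without imputation. SAP section 7 lists no change on this point.

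**The concern.** A window table that suits ECGs and laboratory tests, which are taken at most visits, does not suit a scale rated at three or four of them. A PANSS taken at termination on Day 22 becomes a Week 3 score, and a PSP taken on Day 15 becomes a Week 2 score. Neither label exists among that scale's planned visits, so neither score has a place in a model built on those visits. The data are lost through a labelling convention, not through a decision about whether they belong in the estimand.

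The primary and key secondary analyses are both affected. A patient whose only post-Baseline score gets such a label has no row in the model. Early stopping is not rare in this programme: protocol Table 2 shows that 165 of 244 randomized patients completed the double-blind phase of the Phase 2b study, so 79 (79/244 = 32%) did not. Protocol 9.3 withdraws patients for worsening on PANSS or CGI-S, so termination scores can carry outcome information.

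**Working it through.** The plan gives no figure for this point, and the sample size plays no part in it. What can be reproduced is how Table 1 was built.

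**Table 1.** Target days are 8, 15, 22, 29, 57 and 85 for Weeks 1, 2, 3, 4, 8 and 12. The footnote sets bounds about halfway between targets. The midpoints 11.5, 18.5, 25.5, 43 and 71 give the printed windows: Week 1 Days 3-11 (extended down to Day 3 so that there is no gap), Week 2 Days 12-18, Week 3 Days 19-25, Week 4 Days 26-43, Week 8 Days 44-71, and Week 12 from Day 72.

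**Days with an unplanned label.** Possible termination days are taken as Days 3-84, which is 84 - 3 + 1 = 82 days.
- PANSS: Week 1 (9 days) + Week 3 (7 days) = 16; 16/82 = 20%.
- PSP: Week 1 (9) + Week 2 (7) + Week 3 (7) = 23; 23/82 = 28%.

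Counting Day 2 as well gives 17/83 (20%) and 24/83 (29%). If patients stop only on clinic-visit days (8, 15, 22, 29, 57), the counts are 2 of 5 for PANSS (Days 8, 22) and 3 of 5 for PSP (Days 8, 15, 22). The ±2-day visit tolerance does not change the main counts, because labels depend only on the date of the termination rating.

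**Days on which the lost score is the only one.** This assumes no unscheduled ratings. The first planned PANSS is on Day 15, so a score on any of Days 3-11 is the first and only one: 9 days. By Days 19-25 a Week 2 PANSS already exists. The first planned PSP is on Day 29, so all 23 days qualify.

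**Windows on each scale's own visits, by the same midpoint rule.**
- PANSS and CGI-S, targets 15, 29, 57, 85: midpoints (15+29)/2 = 22, (29+57)/2 = 43, (57+85)/2 = 71.
- PSP, targets 29, 57, 85: midpoints 43 and 71.

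No day then carries an unplanned label. For PANSS, Days 3-11 (9 days) and Days 23-25 (3 days) gain a place outright, 12 of the 16. Days 19-22 (4 days) fall in the Week 2 window, which already holds the planned score. For PSP, all 23 days gain a place.

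**Label shift.** A Day 3 PSP labelled Week 4 moves 29 - 3 = 26 days. A Day 3 PANSS labelled Week 2 moves 15 - 3 = 12 days. The largest PANSS shift is 13 days (Day 44 to 57, or Day 72 to 85), and Table 1 already produces it.

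**The case against.** **The Week 12 row captures terminations.** That row mentions a final or termination visit, and termination is performed as Visit 11. But the footnote attached to the end-of-period label (its marker is not cleanly printed) points to safety tables, and sending every termination score to Week 12 would contradict "All planned, Unscheduled, and Early Termination assessments will be categorized similarly". The text adds ambiguity; it does not cure the problem.

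**The model visits are not listed, so the loss is inferred.** This stands in part. The schedule makes the planned visits the natural choice, but the SAP does not say so. Some figures in SAP 5.2 are not shown and some efficacy table titles are blacked out, so this rests on the readable text. A reader might infer instead that Weeks 1 and 3 enter the model as extra, nearly empty levels, and point to "An unstructured covariance matrix will be used to model the covariance of within-patient scores" as unworkable. No passage proposes such a model.

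**Same-window duplicates are lost too.** With on-schedule visits, a termination PANSS on Days 16-18, 30-43 or 58-71 (3 + 14 + 14 = 31 days), or a PSP on Days 30-43 or 58-71 (28 days), shares a window with an earlier planned score. A reader might add these and conclude that 47 of 82 days (57%) and 51 of 82 (62%) are affected. The documents do not support that sum. SAP 3.3.7 gives a rule: "If assessments are collected multiple times within a given visit window, the result closest to the target day will be used for summary presentations". It is worded for summaries, but with change defined on a single derived-visit value, one value per window is its natural extension to the model. The patient still contributes a score at that visit. Choosing between two values is a convention; having no slot for the only value is a gap.

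**Protocol 10.5 excludes these patients.** It does not. It asks for post-Baseline data, which they have. They drop out only because their score has no row in the model.

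**Some termination scores do not belong.** The estimand targets "The effect of the initially randomized treatment that would have been observed had all patients remained on their treatment throughout the double-blind phase", and a termination rating is taken as soon as possible, not necessarily on drug. This stands: leaving some out may be right, but that should be a stated rule.

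**Conclusion.** The point holds. Followed as written, the window rule gives unplanned labels to termination scores on 16 of 82 days for PANSS and 23 of 82 for PSP. An MMRM on the planned visits then omits them, which does not match protocol 10.5.1. On 9 and 23 of those days the omitted score is the patient's only one after Baseline.

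The assumptions are that the model uses the planned visits and, for the only-score counts, that visits are on schedule and there are no unscheduled ratings. The documents do not give the timing of dropout, so these day counts cannot be turned into patient counts. A reader might infer a biased treatment effect; nothing in the documents gives its size or direction.

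The EMA pattern-mixture analysis is affected only if its predictors use the windowed values. The LOCF analysis already refers to the last post-Baseline measure. This is a cheap improvement to the SAP, not a flaw that undermines the primary analysis.

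**What to change.** Keep Table 1 for safety data and add windows for the efficacy scales in SAP 3.3.7:
- PANSS and CGI-S: Week 2 through Day 22; Week 4 Days 23-43; Week 8 Days 44-71; Week 12 from Day 72.
- PSP: Week 4 through Day 43; Week 8 Days 44-71; Week 12 from Day 72.

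State that only these visits enter the MMRM and the pattern-mixture imputation, that one pre-specified rule picks one value per window, and that the termination text in the Week 12 row does not apply to efficacy. Rerun the primary and key secondary models with the current Table 1 windows as a sensitivity analysis.

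The cost is a few lines, one derivation and one extra run, all before unblinding. The downside is that some scores are labelled later than measured, by up to 13 days for PANSS and 26 for PSP. A termination PANSS on Days 19-22 still competes with the planned Week 2 score; the sensitivity run shows how much the change of windows matters.

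Moving same-window termination scores to the next planned visit is optional. It trades lost data for larger label shifts and is not part of the required change.
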